---------------------------	---

Exclusion Criteria	
Subjects must not meet any of the following exclusion criteria:
 
1. Must not have received prior therapy as follows:
• Chemotherapy or other targeted antileukemic therapy within 7 days of leukapheresis. Hydroxyurea is permitted up to 72 hours prior to leukapheresis.• Hematopoietic growth factors or other immunomodulatory therapy within 7 days of leukapheresis• Systemic steroids within 3 days of leukapheresis, except physiologic steroid replacement with ≤ 0.2 mg/kg/day methylprednisolone or equivalent• Prior therapy including investigational therapy targeted to WT1 such as vaccine therapy or cell therapy• Live vaccine 28 days or fewer prior to planned administration of lymphodepleting therapy2. Subjects with a history of allogeneic HCT are excluded if:
• Subjects are less than 84 days post-transplant, or• Subjects have evidence of ongoing active graft vs host disease (GvHD) requiring systemic immunosuppressants, or• Subjects have received donor lymphocyte infusion (DLI) within 28 days of leukapheresis, or• Subjects are on active immunosuppression for GvHD prophylaxis (must be off for 30 days prior to enrollment). Physiologic steroid replacement with ≤ 0.2 mg/kg/day methylprednisolone or equivalent is permitted.3. [REDACTED]4. Must not have signs or symptoms indicative of central nervous system (CNS) involvement by tumor. A CNS evaluation should be performed to rule out CNS involvement if indicated by signs or symptoms.5. Must not have CNS comorbidity such as transient ischemic attacks, cerebrovascular accident, seizure disorder, or other disorder that could confound neurotoxicity assessments.6. Must not have severe autoimmunity that has required systemic steroid therapy or other immunomodulatory therapy.7. Must not have active disseminated intravascular coagulation (DIC), bleeding or coagulopathy during screening.8. Must be eligible to receive lymphodepleting chemotherapy doses per protocol Section 6.1.3.39. Must not have leukocytosis $\geq 20,000$ WBC/μL despite hydroxyurea or rapidly progressive disease (e.g., recent increase in blast count above 50%) that in the estimation of the investigator or Sponsor would compromise ability to complete study therapy.10. Must have recovered from the acute side effects of their prior therapy, such that eligibility criteria are met.11. Female subjects of childbearing potential are excluded:
a. if unwilling to use protocol specified method of contraception (see Section 13.6) during treatment and for an additional 12 months after administration of NTLA-5001.b. who are breastfeeding or who plan to breastfeed during treatment and for an additional 12 months after administration of NTLA-5001.

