---------------------------	--

	
c. with a positive pregnancy test assessed at screening and/or Day 0 by a highly sensitive urine or serum pregnancy test.
 
12. Male subjects with female partners of childbearing potential or female partners who are pregnant are excluded:
 
a. if unwilling to practice sexual abstinence (refrain from heterosexual intercourse) or use a condom during treatment and for an additional 12 months after the last dose of NTLA-5001.
 
b. if unwilling to abstain from donating sperm during treatment and for an additional 12 months after administration of NTLA-5001.
 
13. Must not have human immunodeficiency virus (HIV) infection, history of Hepatitis B or C infection or positive Hepatitis B surface antigen (HbsAg) or Hepatitis C virus antibody (HCVAb) test, or any uncontrolled infection at screening.
 
14. Must not have any condition, laboratory abnormality, or other reason that, in the investigator's opinion, could adversely affect the safety of the subject, impair the assessment of study results, or preclude compliance with the study.
 
15. Must be willing to comply with study procedures including follow-up as specified by the protocol or unwilling to cooperate fully with the investigator.
 
16. Must not have clinically significant cardiovascular impairment within 12 months of the first dose of study drug, such as history of congestive heart failure greater than New York Heart Association (NYHA) Class II, unstable angina, myocardial infarction, cardiac revascularisation, or cardiac arrhythmia associated with haemodynamic instability.
 
17. [REDACTED]

Retesting During Screening/ Rescreening
	
Retesting During Screening
 
Retesting is defined as repeating laboratory tests within the same screening period. If retesting goes beyond the 28-day screening period, the subject will be classified as a screen failure and will need to go through the rescreening process.
 
Rescreening
 
Subjects who fail to qualify for the study based on laboratory tests may be considered for rescreening at the discretion of the investigator if it is considered that the subject status has changed, and the subject may now qualify for the study. Screening is limited to 2 attempts (initial screening and 1 additional rescreening attempt). A new informed consent is required to be signed prior to rescreening.

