
Dosage and Regimens
	
NTLA-5001
 
NTLA-5001 will be provided as a [REDACTED] cryobags at variable fill volumes to be stored at $\leq -150^{\circ}\text{C}$ in a liquid nitrogen vapor phase container. The study drug will be thawed at 37°C and the dose will be prepared for infusion by qualified site personnel. Study drug preparation details will be provided in the Cell Therapy Manual. Subjects will receive premedication with anti-pyretic and H1 blocker within 1 hour prior to dosing. NTLA-5001 will be administered as an IV infusion at 10-20 mL/min. Total time from thaw to complete administration may not exceed 4 hours.
 
Lymphodepleting chemotherapy
 
Cyclophosphamide will be administered on Day -5, -4, and -3 as intravenous infusion at 500 mg/m^2 each day.
 
Fludarabine will be administered on Day -5, -4, and -3 as intravenous infusion at 30 mg/m^2 each day.

	
For chemotherapy dosing, body surface area (BSA) is calculated based on body weight for subjects weighing up to 120% of ideal body weight (IBW), and BSA is calculated based on adjusted body weight for subjects weighing >120% of IBW. IBW and adjusted weight are determined per institutional standard. Rounding is permitted per institutional standard.

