 - a. if unwilling to use protocol specified method of contraception (see Section 13.6) during treatment and for an additional 12 months after administration of NTLA-5001.
 - b. who are breastfeeding or who plan to breastfeed during treatment and for an additional 12 months after administration of NTLA-5001.
 - c. with a positive pregnancy test assessed at screening and/or day 0 by a highly sensitive urine or serum pregnancy test.
12. Male subjects with female partners of childbearing potential or female partners who are pregnant are excluded:
 - a. if unwilling to practice sexual abstinence (refrain from heterosexual intercourse) or use a condom during treatment and for an additional 12 months after the last dose of NTLA-5001.
 - b. if unwilling to abstain from donating sperm during treatment and for an additional 12 months after administration of NTLA-5001.
13. Must not have human immunodeficiency virus (HIV) infection, history of Hepatitis B or C infection or positive Hepatitis B surface antigen (HbsAg) or Hepatitis C virus antibody (HCVAb) test, or any uncontrolled infection at screening.
14. Must not have any condition, laboratory abnormality, or other reason that, in the investigator's opinion, could adversely affect the safety of the subject, impair the assessment of study results, or preclude compliance with the study.
15. Must be willing to comply with study procedures including follow-up as specified by the protocol or unwilling to cooperate fully with the investigator.
16. Must not have clinically significant cardiovascular impairment within 12 months of the first dose of study drug, such as history of congestive heart failure greater than New York Heart Association (NYHA) Class II, unstable angina, myocardial infarction, cardiac revascularisation, or cardiac arrhythmia associated with haemodynamic instability.
17. [REDACTED]

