6.1.3.3 Lymphodepleting Chemotherapy

Lymphodepleting chemotherapy may be administered in the inpatient or outpatient setting for 3 consecutive days at 24-hour (\pm 3 hours) intervals.

Cyclophosphamide will be administered on Day -5, -4, and -3 as intravenous infusion at 500 mg/m² each day.

Fludarabine will be administered on Day -5, -4, and -3 as intravenous infusion at 30 mg/m² each day.

For chemotherapy dosing, body surface area (BSA) is calculated based on body weight for subjects weighing up to 120% of ideal body weight (IBW), and BSA is calculated based on adjusted body weight for subjects weighing >120% of IBW. IBW and adjusted weight are determined per institutional standard, including the timing of the body weight measurement relative to the chemotherapy dosing. Rounding is permitted per institutional standard.

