8.1.3.1 Criteria for Entering the Study Treatment Phase

Subjects must be reassessed for entry into the study treatment phase within 1 week of lymphodepleting chemotherapy.

Subjects must meet all of the following inclusion criteria:

1. Subject must have a projected life expectancy of at least 6 weeks.
2. Subject must have an ECOG performance status of 0 to 2.
3. Subjects must have adequate organ function defined as:
 - $AST \leq 2.5 \times ULN$ and $ALT \leq 2.5 \times ULN$ (unless considered due to leukemic organ involvement).
 - $Bilirubin \leq 1.5 \times ULN$ (unless considered due to leukemic organ involvement). Note: Subjects with Gilbert's Syndrome may have a bilirubin $> 1.5 \times ULN$ but must have direct bilirubin $\leq 1 \times ULN$.
 - $eGFR \geq 30$ mL/min; determined by CKD-Epi Study equation.

Subjects must not meet any of the following exclusion criteria:

1. Subjects with a history of allogeneic HCT are excluded if:

- Subjects have evidence of ongoing active GvHD, or
 - Subjects are on active immunosuppression for GvHD prophylaxis (must be off for 30 days prior to enrollment). Physiologic steroid replacement with ≤ 0.2 mg/kg/day methylprednisolone or equivalent is permitted.
2. Must not have signs or symptoms indicative of CNS involvement by tumor. A CNS evaluation should be performed to rule out CNS involvement if indicated by signs or symptoms.
 3. Must not have active DIC, bleeding or coagulopathy during screening.
 4. Must be eligible to receive lymphodepleting chemotherapy doses per protocol Section 6.1.3.3
 5. Must not have leukocytosis $\geq 20,000$ WBC/ μ L despite hydroxyurea or rapidly progressive disease (e.g., recent increase in blast count above 50%) that in the estimation of the investigator or Sponsor would compromise ability to complete study therapy.
 6. Must not have any condition, laboratory abnormality, or other reason that, in the investigator's opinion, could adversely affect the safety of the subject, impair the assessment of study results, or preclude compliance with the study.

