13.6 Appendix 6 Contraceptive Guidance and Collection of Pregnancy Information

13.6.1 Definitions

Women of Childbearing Potential (WOCBP)

Women in the following categories are considered WOCBP (fertile):

1. Following menarche
 2. From the time of menarche until becoming postmenopausal unless permanently sterile (see below)
 - A postmenopausal state is defined as no menses for 12 months without an alternative medical cause.
 - A high follicle-stimulating hormone (FSH) level in the postmenopausal range may be used to confirm a postmenopausal state in women not using hormonal contraception or hormonal replacement therapy (HRT). However, in the absence of 12 months of amenorrhea, confirmation with more than 1 FSH measurement is required.
 - Females on HRT and whose menopausal status is in doubt will be required to use 1 of the nonestrogen hormonal highly effective contraception methods if they wish to continue their HRT during the study. Otherwise, they must discontinue HRT to allow confirmation of postmenopausal status before study enrollment.
 - Permanent sterilization methods (for the purpose of this study) include:
 - Documented hysterectomy
 - Documented bilateral salpingectomy
 - Documented bilateral oophorectomy
 - For individuals with permanent infertility due to an alternate medical cause other than the above, (e.g., Mullerian agenesis, androgen insensitivity, gonadal dysgenesis), investigator discretion should be applied to determining study entry.
- Note:** Documentation can come from the site personnel's review of the participant's medical records, medical examination, or medical history interview.
- If fertility is unclear (e.g., amenorrhea in adolescents or athletes) and a menstrual cycle cannot be confirmed before first dose of study intervention, additional evaluation should be considered.

Contraception Guidance:

CONTRACEPTIVES ^a ALLOWED DURING THE STUDY INCLUDE:
Highly Effective Methods ^b That Have Low User Dependency

• Implantable progestogen-only hormone contraception associated with inhibition of ovulation^c

• Intrauterine device (IUD)

• Intrauterine hormone-releasing system (IUS)^c

• Bilateral tubal occlusion

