
• Azoospermic partner (vasectomized or due to a medical cause) Azoospermia is a highly effective contraceptive method provided that the partner is the sole sexual partner of the WOCBP and the absence of sperm has been confirmed. If not, an additional highly effective method of contraception should be used. Spermatogenesis cycle is approximately 90 days. Note: documentation of azoospermia for a male participant can come from the site personnel's review of the participant's medical records, medical examination, or medical history interview.
Highly Effective Methods ^b That Are User Dependent

• Combined (estrogen- and progestogen-containing) hormonal contraception associated with inhibition of ovulation^c
○ oral○ intravaginal○ transdermal○ injectable

• Progestogen-only hormone contraception associated with inhibition of ovulation^c
○ oral○ injectable

a) Contraceptive use by men or women should be consistent with local regulations regarding the use of contraceptive methods for those participating in clinical studies.
 
b) Failure rate of < 1% per year when used consistently and correctly. Typical use failure rates differ from those when used consistently and correctly.
 
c) Male condoms must be used in addition to hormonal contraception. If locally required, in accordance with Clinical Trial Facilitation Group (CTFG) guidelines, acceptable contraceptive methods are limited to those which inhibit ovulation as the primary mode of action.
 
d) True abstinence: When this is in line with the preferred and usual lifestyle of the subject.
 
Note: Periodic abstinence (such as calendar, ovulation, symptothermal, post-ovulation methods), withdrawal (coitus interruptus), spermicides only, and lactational amenorrhea method (LAM) are not acceptable methods of contraception for this study. Male condom and female condom should not be used together (due to risk of failure from friction).

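### No visible criterion requires a repeat negative pregnancy test between screening and lymphodepletion

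*Protocol*

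**What the plan says.** Exclusion 11c reads the same in the Synopsis and in Protocol Section 5.2: a woman of childbearing potential is excluded "with a positive pregnancy test assessed at screening and/or Day 0 by a highly sensitive urine or serum pregnancy test". It names two points, screening and Day 0.

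The Synopsis (Dosage and Regimens) places the chemotherapy between them: "Cyclophosphamide will be administered on Day -5, -4, and -3 as intravenous infusion at" a stated daily dose, with fludarabine on the same three days. Section 6.1.3.3 adds that "Lymphodepleting chemotherapy may be administered in the inpatient or outpatient setting for 3 consecutive days".

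The check before chemotherapy is in Section 8.1.3.1: "Subjects must be reassessed for entry into the study treatment phase within 1 week of lymphodepleting chemotherapy". It has 3 inclusion and 6 exclusion items, and none mentions pregnancy. The eligibility note in Table 1-1 of the Schedule of Activities sends the reader to this list.

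Other provisions bear on the risk:
- Exclusion 11a removes women "if unwilling to use protocol specified method of contraception (see Section 13.6) during treatment and for an additional 12 months" after NTLA-5001. The Section 13.6.1 methods table is headed as contraceptives "ALLOWED DURING THE STUDY INCLUDE", and a footnote describes the highly effective methods: "Failure rate of < 1% per year when used consistently and correctly".
- Table 13-1 lists a serum pregnancy test at screening and urine tests at later visits, without saying which visits.
- The focused examination in Table 1-1 includes a question about conception.
- Exclusion item 6 of Section 8.1.3.1 lets the investigator stop a subject for any safety-relevant condition or laboratory finding.

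**The concern.** The protocol accepts that screening data age. Within a week of chemotherapy it rechecks performance status, organ function, GvHD, CNS signs, coagulopathy and white cell count. It also repeats the marrow in several situations, one being more than 6 weeks since the screening sample. Pregnancy status gets no such recheck in any criterion that can be read.

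The second named test does not protect against the chemotherapy. A woman whose first positive result comes on Day 0 would be kept from NTLA-5001 after all three days of cyclophosphamide and fludarabine. The documents do not discuss fetal risk from these drugs. I take it as given that they should not be started in an unrecognised pregnancy. No endpoint, analysis or dose decision is affected; the stake is the safety of an individual subject and a fetus.

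**Working it through.** There is no figure of the plan's own to reproduce. The check compares texts and then bounds the size of the risk.

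**1. Order of events.** From the Synopsis and Sections 5.2, 6.1.3.3 and 8.1.3.1:

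| Point | Timing | Pregnancy result named in a criterion? |
|---|---|---|
| Screening | up to 28 days before enrollment | Yes (11c) |
| Reassessment | within 1 week before Day -5 | No |
| Chemotherapy | Day -5, -4, -3 | No |
| NTLA-5001 | Day 0 | Yes (11c) |

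Day 0 is 5 days after the first chemotherapy dose and 3 days after the last.

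**2. What the gate carries over.** The six exclusions in Section 8.1.3.1 correspond, in whole or in part, to entry exclusions 2 (prior transplant and GvHD), 4 (CNS disease), 7 (DIC or bleeding), 8 (fit for lymphodepletion), 9 (leukocytosis or rapid progression) and 14 (investigator judgment). Exclusion 11 is absent. Item 4 refers to Section 6.1.3.3, which covers doses, timing and body surface area and says nothing on pregnancy.

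**3. Age of the screening test at Day -5.** Section 6.1.3.2 recommends nine optional bridging agents, given after leukapheresis: one with a 72-hour washout, four with 2 weeks and four with 4 weeks. Days for leukapheresis, bridging itself and manufacturing are not given and are left out, so these are lower limits.
- 4-week agent: more than 28 days; more than 28 + 28 = 56 days if tested on the first day of a full 28-day screening period.
- 2-week agent: more than 14 days; more than 28 + 14 = 42 days on the same basis.
- No bridging: not computable. Section 8.1.2 does foresee more than 6 weeks (42 days) since the screening marrow.

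**4. Probability of a new pregnancy in the gap.** Formula: annual rate × days / 365.25. The rate is the protocol's ceiling of 1% per year with correct use, credited for the whole interval.
- 28 days: 1% × 28/365.25 = 0.077%
- 42 days: 1% × 42/365.25 = 0.115%
- 56 days: 1% × 56/365.25 = 0.153%

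Extreme case: if all 54 planned subjects were women of childbearing potential with 56-day gaps, the expected number is below 54 × 0.153% = 0.083.

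**5. Sensitivity to imperfect use.** The protocol says typical-use rates differ but gives none. If 5% to 10% per year is assumed (my range, not the documents'), 56 days gives 5% × 56/365.25 = 0.77% to 10% × 56/365.25 = 1.53% per woman. All these figures rise in proportion if the gap is longer.

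**The case against.** The strongest reply is that the test may already be scheduled. Most laboratory rows of Tables 1-1 and 1-2, where a pregnancy row would sit, are missing from the text available to me. Table 13-1 calls for urine tests after screening, and both the reassessment and Day -5 come after screening. Section 8 makes the Schedule binding. A positive result could then be acted on under item 6 of Section 8.1.3.1, and 11c leaves no doubt that pregnancy excludes. Bridged subjects are also under their physicians' standard-of-care assessments (Section 8.1.2).

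This rules out any claim that no test is done before chemotherapy, and I make none. It does not answer the narrower point. Table 13-1 names no visit and attaches no consequence to a positive result. Item 6 is discretionary and requires no test. A history question can miss an early pregnancy, and the standard-of-care assessments are not specified. Even with a scheduled test, no visible criterion would make its result a stated exclusion from chemotherapy.

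The reply on size is right. Both sexes are enrolled, Section 2.2.1 describes AML as mainly a disease of older adults, and Section 13.6.1 requires condoms alongside hormonal methods. The 54-subject figure is therefore an extreme. SAP Section 7 also records that the sponsor terminated the study with only 2 subjects dosed, so the practical use is mainly for criteria reused in a later protocol.

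**Conclusion.** The point holds, as a minor one. Exclusion 11c names only screening and Day 0, chemotherapy is complete by Day -3, and the gate before chemotherapy does not carry over exclusion 11. The event is rare: below about 0.15% per woman over 56 days with correct contraception, and fewer than 0.09 expected pregnancies in the extreme case. Under the assumed typical-use range it would be about 0.8% to 1.5% per woman.

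The probabilities rest on contraception being in use throughout the gap. Exclusion 11a speaks of the treatment period, while the methods table speaks of the study. They also depend on the gap length, which has no stated upper limit. The share of women of childbearing potential is not given. Confidence is medium, because the missing Schedule row decides whether the fix adds a test or only gives an existing test a stated consequence.

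**What to change.** First check the pregnancy row of the Schedule of Activities. Then:

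1. Add to the Section 8.1.3.1 exclusions, for women of childbearing potential: *a positive highly sensitive urine or serum pregnancy test at the reassessment within 1 week before lymphodepleting chemotherapy*.
2. In exclusion 11c, in both the Synopsis and Section 5.2, change the timing to *at screening, before lymphodepleting chemotherapy, and/or Day 0*.
3. If the Schedule has no pregnancy test at the reassessment, add one.

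The cost is the wording plus at most one urine test per woman of childbearing potential, at a visit that already exists. If the test is already scheduled there, the cost is wording alone. Endpoints, sample size and dose escalation are unchanged.

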1.2 Schema

DLT = dose limiting toxicities

1.3 Schedule of Activities (SoA)

Table 1-1 Schedule of Activities: Screening Through Day 14 (In Patient Observation)

Study Period	SCR ^a	LP Reassessment	Lymphodepletion							Treatment and Observation							Notes	
			-12 to -6	-5	-4	-3	0	1	2	3	4	5	6	7	8-14 ^b			
General and Safety Assessments																		
Signing of informed consent	X																	
Eligibility criteria	X	X ^{*d}																*Assessment of eligibility to enter treatment phase should be performed within 1 week prior to Day -5 (see Section 8.1.3.1).
Medical history	X																	
Demographics	X																	
Full physical examination	X																	
Focused physical examination		X						X	X	X	X	X	X	X	X	X	X	Focused exam will be symptom based. The PI will inquire if the subject has experienced testicular/scrotal pain, swelling, and erythema for males and lower abdominal pain or vaginal bleeding for women, or any reproductive symptoms, whether the subject is trying to conceive, or has successfully conceived. Should a pregnancy occur a detailed in-utero assessment will be performed. Physical exam at each clinic visit will assess for any new pleural or peritoneal effusions.
ECOG assessment	X	X ^d																X [*] : Prior to beginning lymphodepletion
Vital signs	X				X			X	X	X	X	X	X	X	X	X	X	
Weight	X				X			X	X	X	X	X	X	X	X	X	X	
Chest x-ray	X																	
Echocardiogram	X																	
Prior and concomitant medications	X	X			X			X	X	X	X	X	X	X	X	X	X	Includes RBC and platelet transfusions.
Adverse event assessment	X	X			X			X	X	X	X	X	X	X	X	X	X	

Table 1-1 Schedule of Activities: Screening Through Day 14 (In Patient Observation) (continued)

Study Period	SCR ^a LP	Reassessment	Lymphodepletion							Notes									
			-12 to -6	-5	-4	-3	0 ^e	1	2		3	4	5	6	7	8-14 ^b			
Laboratory Assessments																			
PBMC	X							X*	X					X	X	X*	X*	Collect 1 hour post-infusion. For subjects at the site on Day 9, 10, and/or 11, one additional sample should be collected as close as possible to Day 11.	
Efficacy Assessments																			
Bone marrow sampling and PBMC morphology	X ^c	X**																X*: Includes cytogenetic and molecular profiling. X**: Repeat assessment prior to beginning LD chemotherapy if no sample was obtained after signing consent, or >6 weeks since SCR BM or warranted by change in clinical condition or if subject has received bridging therapy other than hydroxyurea.	
Study Arm assessment	X	X*																Study Arm assessment will be determined by the investigator. X*: Repeat assessment of Study Arm eligibility if repeat BM done.	
EORTC QLQ-C30	X																		
Study-required Procedures and Treatment																			
Leukapheresis		X																	Permitted if clinically indicated during the LP/cell manufacturing period. This bridging therapy may take place between leukapheresis and treatment. Any treatment required for bridging therapy will be collected on the concomitant medications CRF. See Section 6.1.3.2 for washout periods.
Bridging therapy (if clinically required)		X																	Assessment of eligibility to enter treatment phase should be performed within 1 week prior to Day -5 (see Section 8.1.3.1)
Meets entry and exclusion for treatment phase		X																	Lymphodepleting chemotherapy may be administered in the Inpatient or Outpatient setting. See Section 6.1.3.3
Lymphodepleting chemotherapy				X	X	X													Administer within 1 hour of NTLA-5001 dosing (see Section 6.1.3 for details).
Premedication								X											
NTLA-5001 dosing									X										
In unit observation								X	X	X	X	X	X	X	X	X	X*		X*: Only UK subjects are required to be hospitalized for days 8-14.

Note: All assessments on Day 0 are performed prior to infusion, unless otherwise indicated.

██████████ AML = acute myeloid leukemia; BM = bone marrow; CK = cell kinetics; CRF = case report form; ECOG = Eastern Cooperative Oncology Group; EORTC QLQ-C30 = European Organization for Research and Treatment of Cancer Quality of Life Questionnaire; LD = lymphodepletion; LP = leukapheresis; PBMC = peripheral blood mononuclear cell; PCR = polymerase chain reaction; RBC = red blood count; SCR = screening; SARS-CoV-2 = severe acute respiratory syndrome coronavirus 2

- a. The screening period will be up to 28 days prior to enrollment.
- b. In-patient observation on days 8-14 is required for UK subjects only.
- c. Bone marrow samples collected after the completion of all prior therapy and prior to signing consent are allowed so long as the required bone marrow assessments were completed. Potential Arm 2 subjects: For subjects with $\geq 5\%$ bone marrow blasts, morphology by local assessment is sufficient for eligibility. If a marrow sample collected prior to signing consent is used for enrollment, a bone marrow sampling and PBMC morphology is required between leukapheresis/bridging therapy completion and the initiation of lymphodepleting chemotherapy. Potential Arm 1 subjects: For subjects with $< 5\%$ bone marrow blasts, MRD measurement by the central vendor is needed to determine eligibility. Therefore, a bone marrow sample during screening is required.
- d. Subjects must be reassessed for entry into the study treatment phase within 1 week of lymphodepleting chemotherapy. Please see Section 8.1.3.1
- e. All D0 blood and urine collections should be completed as close as possible to the indicated time.

Table 1-2 Schedule of Activities: Assessment Phase Through End of Study (continued)

Study Period	Assessment Phase							EOS	Notes				
	2	4	8	16	28	40	52			64	76	88	100
Study Week	2	4	8	16	28	40	52	64	76	88	100	112	
Visit Window (days)	±2		±4		±7 days								
Laboratory Assessments (continued)													
vector shedding (urine)	X	X	X	X	X								X
Cytokines (plasma)	X	X	X	X	X								
Cell kinetics	X	X	X	X	X	X	X	X	X	X	X	X	X
PBMC	X	X	X	X	X	X	X	X	X	X	X	X	X
Efficacy Assessments													
Bone marrow sampling and PBMC morphology*	X	X	X	X	X	X	X	X	X	X	X	X	X
Disease response assessment	X	X	X	X	X	X	X	X	X	X	X	X	X
EORTC QLQ-C30	X	X	X	X	X	X	X	X	X	X	X	X	X

*: Includes cytogenetic and molecular profiling and flow cytometry for AML MRD.
 At the investigator's discretion, an early bone marrow aspirate and biopsy may be performed at the Week 2 visit. BM sampling is to be performed until the subject achieves complete remission and has no evidence of MRD. Thereafter, subjects should undergo bone marrow sampling every 12 weeks for 1 year after remission is first documented. Subsequently, subjects in CR are not required to have additional bone marrow sampling unless clinically indicated.
 Refer to Section 13.4 for guidance.

AE = adverse event; AML = acute myeloid leukemia; BM = bone marrow; CK = cell kinetics; ECOG = Eastern Cooperative Oncology Group; EORTC QLQ-C30 = European Organization for Research and Treatment of Cancer Quality of Life Questionnaire; EOS = end of study; PBMC = peripheral blood mononuclear cell; MRD = measurable residual disease; PCR = polymerase chain reaction; SARS-CoV-2 = severe acute respiratory syndrome coronavirus 2

Table 1-3 Schedule of Activities: Safety Follow Up Visits for Subjects No Longer Receiving Clinical Benefit

Study Period	Safety Assessment Phase										Notes	
	16	28	40	52	64	76	88	100	112			
Study Week												
Visit Window	±7 days											
Focused physical examination	X	X	X	X	X	X	X	X	X	X	X	Focused exam will be symptom based. The PI will inquire if the subject has experienced testicular/scrotal pain, swelling, and erythema for males and lower abdominal pain or vaginal bleeding for women, or any reproductive symptoms, whether the subject is trying to conceive, or has successfully conceived. Should a pregnancy occur a detailed in-utero assessment will be performed. Physical exam at each clinic visit will assess for any new pleural or peritoneal effusions.
Vital signs	X	X	X	X	X	X	X	X	X	X	X	
Weight	X	X	X	X	X	X	X	X	X	X	X	
Adverse event assessment	X	X	X	X	X	X	X	X	X	X	X	Treatment-related adverse events and treatment-related serious adverse events only

PI = principal investigator

TABLE OF CONTENTS

TITLE PAGE	1
INVESTIGATOR STATEMENT	2
CONTACT DETAILS OF KEY PERSONNEL.....	3
1 PROTOCOL SUMMARY.....	4
1.1 Synopsis	4
1.2 Schema.....	15
1.3 Schedule of Activities (SoA)	16
TABLE OF CONTENTS.....	23
LIST OF ABBREVIATIONS.....	27
2 INTRODUCTION	31
2.1 Study Rationale.....	31
2.2 Background.....	32
2.2.1 Disease Background.....	32
2.2.2 NTLA-5001 Investigational Product Background.....	32
2.2.3 NTLA-5001 Nonclinical Information.....	33
2.3 Benefit/Risk Assessment	34
2.3.1 Risk Assessment	34
2.3.2 Benefit Assessment.....	38
2.3.3 Overall Benefit: Risk Conclusion.....	38
3 STUDY OBJECTIVES AND ENDPOINTS.....	39
4 STUDY DESIGN AND DOSE RATIONALE	40
4.1 Overall Study Design.....	40
4.1.1 Replacement of Subjects.....	41
4.1.2 Screen Failures.....	41
4.1.3 Dose Rationale.....	41
4.2 End of Study	41
5 STUDY POPULATION.....	43
5.1 Inclusion Criteria	43
5.2 Exclusion Criteria	44
5.3 Criteria for Entering the Study Treatment Phase.....	46
6 STUDY TREATMENT(S).....	47
6.1 Study Treatment(s) Administered.....	47
